1. PROTOCOL SYNOPSIS FOR STUDY 205920

Rationale

Post-partum hemorrhage is one of the main causes of maternal mortality in the developing world. The World Health Organization (WHO) lists oxytocin on its list of ‘Essential Medicines’ for Humanity as a preventative treatment for post-partum hemorrhage; however, because of its cold-chain storage requirement and parenteral administration route, high-quality oxytocin is not always available in resource-poor settings. GlaxoSmithKline (GSK) has developed a stable, dry-powder formulation of oxytocin to address this unmet need, with the goal of reducing post-partum hemorrhage morbidity and mortality in these settings.

This study is being conducted to further assess safety and tolerability of inhaled oxytocin, and to characterize the pharmacokinetic (PK) profile of inhaled oxytocin compared to oxytocin administered as standard of care. Two groups of subjects will be enrolled. Group 1 will enroll pregnant women, who will be randomized to receive either inhaled (IH) or intramuscular (IM) oxytocin as active management of the third stage of labour. Group 2 will enroll non-pregnant women of childbearing potential, who will receive IH oxytocin and intravenous (IV) oxytocin in a cross over design over two dosing sessions.

Objectives/Endpoints

Group 1 – Women in Third Stage of Labour (TSL)

Objectives	Endpoints
Primary	

 To characterize the pharmacokinetics of single doses of IH oxytocin and 10 International Units (I.U.) IM oxytocin in women in TSL. 	
 Plasma concentration time profile for IH oxytocin and 10 I.U. IM oxytocin. PK parameters: Maximum observed plasma concentration (C_{max}), Observed plasma concentrations at 10 minutes (min) post-dose (C_{p10}), Observed plasma concentrations at 20 min post-dose (C_{p20}), Observed plasma concentrations at 30 min post-dose (C_{p30}), Time to C_{max} (t_{max}), Area under concentration-time curve (AUC), and Terminal phase half-life (t_{1/2}) will be calculated as data permit.
Secondary	

 To evaluate the safety and tolerability of inhaled oxytocin. 	
 General safety parameters: adverse events (AE); absolute values and changes over time of vital signs (blood pressure, heart rate, respiratory rate, temperature).

 To compare pharmacokinetics of IH oxytocin to 10 I.U. IM oxytocin in women in TSL. 	
 C_{max}, C_{p10}, C_{p20}, C_{p30}, Area under the concentration-time curve from time zero (pre-dose) to three hours (h) (AUC_[0-3h])

Objectives	Endpoints
	will be compared as data permit.
Exploratory	

 Pharmacodynamic effect of IH oxytocin and 10 I.U. IM oxytocin in women in TSL. 	
 Pre and post-delivery haemoglobin.

 Participant feedback regarding ease of use, instructions, and perceived ability of patients to use the ROTHALER. 	
 Questionnaire results from participants.

Group 2 – Non-pregnant, non-lactating females of child bearing potential

[figure not shown]
Objectives	Endpoints
Primary	

 To evaluate the safety and tolerability of IH and IV oxytocin. 	
 General safety parameters: adverse events; absolute values and changes over time of vital signs (blood pressure, heart rate) and 12-lead electrocardiogram (ECG) parameters (PR, QRS, QT, Corrected QT interval [QTc] intervals) from pre-dose values. Specific respiratory safety parameters: adverse respiratory events as monitored by spirometry including Forced expiratory volume at 1 minute (FEV1.0), respiratory rate, and pulse oximetry.

 To characterize the pharmacokinetics of single doses of IH oxytocin and 5 I.U. IV oxytocin. 	
 Plasma concentration time profile for IH oxytocin and 5 I.U. IV oxytocin. PK parameters: C_{max}, C_{p10}, C_{p20}, C_{p30}, t_{max}, AUC, Plasma clearance (CL), volume of distribution and t_{1/2} will be calculated as data permit.
Exploratory	

 To evaluate endogenous plasma oxytocin concentrations in non-pregnant females in the presence and absence of the combined oral contraceptive. 	
 Pre-dose plasma concentrations of oxytocin.

 To compare the IH pharmacokinetics of oxytocin between Cohort A (subjects on combined oral contraceptive) and Cohort B (subjects using a non-hormonal form of contraception). 	
 C_{p10}, C_{p20}, C_{p30}, C_{max}, AUC(0-3h), Area under the concentration-time curve from time zero to infinity (AUC[0-∞]) and t_{1/2}, will be compared as data permit.

 To compare the IV pharmacokinetics of oxytocin between Cohort A and Cohort B. 	
 C_{max}, AUC, t_{1/2}, CL and Volume of distribution (VOD) will be compared as data permit.

Groups 1 and 2 – Women in TSL and Non-pregnant, non-lactating females of child bearing potential

[figure not shown]
Objectives	Endpoints
Exploratory	

 To compare pharmacokinetics of IH oxytocin between Group 1 and Group 2 	
 Cp10, Cp20, Cp30, Cmax, AUC(0-3h) AUC(0-∞), and t1/2 will be compared as data permit.

Overall Design

Group 1 – Women in TSL

Group 2 – Non-pregnant, non-lactating females of child bearing potential

Treatment Arms and Duration

Screening	
Group 1: All screening assessments to be completed after the 18th week of pregnancy (based on estimated date of delivery).
 
Group 2: All screening assessments to be completed within 28 days prior to the first dose.

Treatment Session	
Group 1: Each subject will take part in 1 dosing session.
 
Group 2: Each subject will take part in 2 dosing sessions.

Treatment Arms ¹	
Group 1: Subjects will be randomised to receive one of the following study treatments:
 
 • 400 micrograms (mcg) IH oxytocin • 10 I.U. IM oxytocin 
Group 2: Subjects will receive both of the following study treatments over the course of two dosing sessions:
 
 • 400 mcg IH oxytocin • 5 I.U. IV oxytocin
Follow-up	
Group 1: Follow Up 1 – Within approximately 24 h post dose.
 
Group 1: Follow Up 2 – At least 7 days and no greater than 14 days after study drug administration.
 
Both visits may be conducted in-person or via telephone.
 
Group 2: At least 7 days and no greater than 21 days after last study drug administration.
 
This visit will be conducted in-person.
 
If warranted, additional follow-up visits may be scheduled for both Groups.

Total Duration	
Group 1: Screening after 18th week of pregnancy (i.e. within 168 days of 1 dosing session) + follow up of 7 - 14 days = approximately 183 days
 
Group 2: Screening within 28 days of dosing session 1 + 2 dosing sessions with a maximum of 14 days between dosing + follow-up of 7 – 21 days = 64 days

Type and Number of Subjects

Sufficient subjects will be screened such that approximately 20 subjects complete all study procedures in Group 1, and approximately 10 subjects complete all study procedures in Group 2 (approximately 5 in each cohort of Group 2).

If subjects prematurely discontinue the study, additional replacement subjects may be recruited and assigned to the same treatment sequence at the discretion of the Sponsor. Replacement subjects will complete all study procedures.

If the PK variability between subjects in Group 1 is higher than expected, it may be required to increase the sample size up to a maximum of 10 additional subjects per treatment group for inhaled and intramuscular oxytocin. In the event of this, sufficient subjects will be screened such that a maximum of 50 subjects complete Group 1.

If a dose adjustment is required in either group, additional subjects may be recruited such that a full 10 subjects receive the final IH or IV dose.

Analysis

The primary objective of this study is to characterize pharmacokinetics of IH oxytocin and IM oxytocin in women in the third stage of labour.

No formal hypotheses will be tested, however, comparisons of interest, within Group 1, and between Group 1 and Group 2 and between Cohorts A and B in Group 2 will be made and the point estimates and corresponding two-sided 90% confidence intervals (CI) will be presented to provide the range of plausible values for the comparisons.

2. INTRODUCTION

Maternal mortality associated with postpartum hemorrhage (PPH) is one of the major public health problems in the developing world. Approximately half a million women worldwide die annually from causes directly related to pregnancy and childbirth, and up to one third of these deaths in Africa and Asia are caused by complications as a result of PPH [Khan, 2006; WHO, 2010]. A Cochrane Review meta-analysis of the data from multiple preventative trials with oxytocin at 10 international units (I.U.) given via the intramuscular (IM) route has confirmed this specific uterotonic, and this particular route of administration, to be the gold standard prophylactic therapy for PPH [Mousa, 2014]. For this reason, the World Health Organization (WHO) has designated oxytocin as one of its 'Essential Medicines' for humanity [WHO Model List of Essential Medicines 18th list, April 2013 (WHO, 2013); WHO Model List of Essential Medicines for Children 4th list, April 2013 (WHO, 2013)].

However, in resource-poor settings within the developing world, the effectiveness of prophylactic IM oxytocin is diminished by a lack of appropriate refrigeration facilities and availability of trained health care professionals (HCPs) to administer IM injections [Mousa, 2014]. Although single-use, oxytocin prefilled, syringes for IM injection are available in many developing countries (e.g. UNIJECT device), the development of a needle-free and self-administered inhaled (IH) oxytocin product, which delivers

comparable systemic exposure to 10 I.U. IM, would be a major step-change in the administration of this life-saving medicine to pregnant women in resource-poor regions of the developing world. This would be particularly relevant in rural areas where the mother has no routine access to a trained HCP and/or where there is no reliable electricity supply to permit refrigerated storage of oxytocin injection vials.

We have developed a stable, dry-powder formulation of oxytocin to be administered via the oral inhaled pulmonary route (compared to 10 I.U. of IM oxytocin) using a GlaxoSmithKline (GSK)-manufactured medical device (or device manufactured for GSK by a third party) which is a capsule-based inhaler (Modified Air Inlet ROTAHALER™ Dry Powder Inhaler (DPI) device, hereafter referred to as ROTAHALER). This formulation and delivery method has the potential to be used in settings where effective oxytocin is currently unavailable to women in the third stage of labour (TSL).

[figure not shown]
2.1. Study Rationale

This study will be the second investigation of oxytocin in humans via the IH route, which follows the first time in human (FTIH) study, 201558 [GlaxoSmithKline Document Number 2015N234711_01, 2015; see Section 2.2.1 for more information on the FTIH trial]. Published literature on the pharmacokinetics (PK) of oxytocin in non-pregnant and pregnant women is limited. There is some evidence to suggest that the metabolic clearance of oxytocin may increase during pregnancy; potentially related to degradation by the circulating aminopeptidase, oxytocinase, and/or pregnancy related changes in hepatic and renal function [Syntocinon Summary of Product Characteristics, Novartis, 2014; Thornton, 1990]. In addition, endogenous oxytocin plasma concentrations have been reported to either increase or remain constant after the delivery of the fetal anterior shoulder [Thornton, 1988]. As a result of these pregnancy related changes, systemic exposure to oxytocin may differ between healthy non-pregnant women and women in the TSL for a given dose and route of administration of oxytocin. To further understand the effect of pregnancy on the PK of oxytocin, this study will investigate the PK of oxytocin in pregnant women in TSL following either IH (400 micrograms [mcg]) or 10 I.U. IM (17 mcg) administration. A greater understanding of the PK of oxytocin in TSL will help facilitate extrapolation of data obtained in healthy non-pregnant women to women in TSL. An additional group of non-pregnant non-lactating female volunteers will also be included as a control group and will receive 400 mcg IH oxytocin and 5 I.U. intravenous (IV) oxytocin. This second group will enrol one cohort of subjects taking the combined oral contraceptive (COC), and another cohort using a non-hormonal form of contraception. This will assess if women need to be on an oral contraceptive vs. other methods of birth control in future clinical studies, since although the COC is believed to suppress endogenous oxytocin levels the literature is not consistent about this observation. As the requirement to be taking the COC makes recruitment more of a challenge it will be helpful to know if this inclusion is essential, or if women using non-hormonal forms of birth control might also have sufficiently low systemic oxytocin levels suitable for PK studies.

2.2. Brief Background

Oxytocin is a nonapeptide which is produced by the hypothalamus and released into the systemic circulation by the posterior pituitary gland. Within the brain, oxytocin, like most hypothalamic synthesized hormones, acts as a neurotransmitter. In human pregnancy, during the later phases of the third trimester, increasing circulating levels of oxytocin act as a potent endogenous uterotonic which facilitates the initiation of labour. Furthermore, a neurohormonal positive feedback loop exists between dilatation of the cervico-vaginal canal by fetal passage and the hypothalamus (i.e. Ferguson reflex) which augments oxytocin production, thus increasing uterine contraction intensity and frequency which facilitates vaginal delivery. However, once the fetus is delivered, plasma oxytocin levels rapidly diminish probably due to a combination of increased circulating levels of oxytocinase (the principal oxytocin deactivating enzyme), in the plasma, an overall reduction in hypothalamic oxytocin synthesis (Figure 1), and a reduction in uterine oxytocin receptor (OTR) density. This oxytocin-depleted, relatively auterotonic, physiological environment puts the mother at risk of PPH during the subsequent placental delivery phase (i.e. TSL).

Figure 1 Oxytocin During Physiological Fetal Delivery

Oxytocin receptors are constitutively expressed in smooth muscle cells (SMCs) in the uterine myometrium, muscular walls of the bronchi and upper digestive tract, myoepithelial cells of the breast duct which are essential for the oxytocin-dependent postpartum breast milk let-down reflex, and in different regions of the brain. Although

uterine OTR expression increases during the later stages of pregnancy, it is not known whether pregnancy increases OTR expression at non-uterine sites, such as the maternal brain, where neuronal oxytocin signalling has been implicated in postpartum bonding behaviour with the baby. Within the kidney, oxytocin is known to bind to vasopressin (V2) receptors, rather than OTR, in the medullary renal collecting duct which triggers an antidiuretic effect.

Binding of oxytocin to OTR triggers an increase in intracellular calcium (Ca²⁺), which is partly mediated through oxytocin-dependent up-regulation of prostaglandin F (PGF)₂ α synthesis, which in the uterine myometrium leads to physiological uterine contractions during 3rd-stage labour.

More recent research has shown oxytocin to be present in broncho-alveolar lavage fluid collected from the respiratory tract of adult humans of both sexes, but oxytocinase expression was not assessed. In an in vivo pharmacology study [Prankerd, 2013] in pregnant ewes intratracheal insufflation of a dry-powder formulation of oxytocin was associated with poor absolute bioavailability (ca 5%), but despite low systemic exposure, this still caused a pharmacodynamic response that was manifested by increased electrical uterine activity measured by electromyography, probably as a result of increased OTR stimulation in the pregnant uterus.

2.2.1. IH Oxytocin FTIH Study 201558

Study 201558 [GlaxoSmithKline Document Number [2016N277949_00](#)] was the FTIH study to evaluate safety, tolerability, and characterize the PK profile of 4 dose strengths of IH oxytocin compared to oxytocin 10 I.U. IM. The study enrolled 16 healthy, non-pregnant, premenopausal female subjects. One subject was withdrawn prior to IH oxytocin dosing due to inability to cannulate. Subjects were administered 10 I.U. IM oxytocin, IH placebo containing (only) the excipients found in the IH oxytocin formulation, and IH oxytocin. A minimum washout period of 48 hours (h) was required between each dose of active drug. This dose escalation study evaluated 4 doses of IH oxytocin: 50 mcg, 200 mcg, 400 mcg, and 600 mcg. The most frequently reported Adverse Event (AE) was headache, and occurred in at least one subject in each treatment arm. In general, IH oxytocin was well-tolerated, no safety concerns with IH dosing were identified, no clinically significant effect on respiratory parameters were observed, and no Serious Adverse Events (SAEs) were reported. The PK profile of the 400 mcg IH oxytocin dose was similar to that of 10 I.U. IM, and has been selected for further evaluation. See Section [4.5](#) for further information on PK characteristics.

2.2.2. PK Specimen Stability as Observed in 205920

Prior to the initiation of the current trial, a sample-handling process was developed using blood from pregnant subjects of at least 37 weeks gestation to ensure ex-vivo oxytocin stability in specimens collected from Group 1 TSL subjects.

Per protocol, after 10 subjects had completed all procedures in Group 1, an informal interim PK analysis was conducted. It was observed that in the majority of the plasma samples collected from TSL subjects, oxytocin concentrations were below the limit of quantification (BLQ) or at very low concentrations (approximately 3pg/mL) approaching

the lower limit of quantification (LLQ) of the assay (2pg/mL). This was seen across both IM and IH routes of administration. This was an unexpected finding which has been confirmed by re-analysis of selected samples. As such, it is considered that it may be due to ex-vivo oxytocin instability related to uninhibited oxytocinase and peptidases, which are believed to be at increased concentrations in the plasma of postpartum women compared with non-pregnant women, and women at 37 weeks gestation. This finding resulted in a temporary halt to the trial.

3. OBJECTIVES AND ENDPOINTS

3.1. Group 1: Women in TSL

Objectives	Endpoints
Primary	

 To characterize the pharmacokinetics of single doses of IH oxytocin and 10 I.U. IM oxytocin in women in TSL. 	
 Plasma concentration time profile for IH oxytocin and 10 I.U. IM oxytocin. PK parameters: Maximum observed plasma concentration (C_{max}), Observed plasma concentrations at 10 minutes (min) post-dose (C_{p10}), Observed plasma concentrations at 20 min post-dose (C_{p20}), Observed plasma concentrations at 30 min post-dose (C_{p30}), Time to C_{max} (t_{max}), Area under concentration-time curve (AUC), and Terminal phase half-life (t_{1/2}) will be calculated as data permit.
Secondary	

 To evaluate the safety and tolerability of inhaled oxytocin. 	
 General safety parameters: adverse events; absolute values and changes over time of vital signs (blood pressure, heart rate, respiratory rate, temperature).

 To compare pharmacokinetics of IH oxytocin to 10 I.U. IM oxytocin in women in TSL. 	
 C_{max}, C_{p10}, C_{p20}, C_{p30}, Area under the concentration-time curve from time zero (pre-dose) to three hours (h) (AUC[0-3h]) will be compared as data permit.
Exploratory	

 Pharmacodynamic effect of IH oxytocin and 10 I.U. IM in women in TSL. 	
 Pre and post-delivery haemoglobin.

 Participant feedback regarding ease of use, instructions, and perceived ability of patients to use the ROTHALER. 	
 Questionnaire results from participants.

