4.2. Treatment Arms and Duration

Screening	
Group 1: All screening assessments to be completed after the 18th week of pregnancy (based on estimated date of delivery)
 
Group 2: All screening assessments to be completed within 28 days prior to the first dose

Treatment Session	
Group 1: Each subject will take part in 1 dosing session.
 
Group 2: Each subject will take part in 2 dosing sessions

Treatment Arms ¹	
Group 1: Subjects will be randomised to receive one of the following study treatments:
 
 • 400 mcg IH oxytocin • 10 I.U. IM oxytocin 
Group 2: Subjects will receive both of the following study treatments over the course of two dosing sessions:
 
 • 400 mcg IH oxytocin • 5 I.U. IV oxytocin
Follow-up	
Group 1: Follow Up 1 – Within approximately 24 hours post dose.
 
Group 1: Follow Up 2 – At least 7 days and no greater than 14 days after study drug administration.
 
Both visits may be conducted in-person or via telephone. Group 2: At least 7 days and no greater than 21 days after last study drug administration.
 
This visit will be conducted in-person.
 
If warranted, additional follow-up visits may be scheduled for both Groups.

Total Duration	
Group 1: Screening after 18th week of pregnancy (i.e. within 168 days of 1 dosing session) + follow up of 7 - 14 days = approximately 183 days
 
Group 2: Screening within 28 days of dosing session 1 + 2 dosing sessions with a maximum of 14 days between dosing + follow-up of 7 – 21 days = 64 days

¹ See Section 6.4 for possible dose adjustment to IH oxytocin.

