4.5. Dose Justification

Single inhaled doses of oxytocin (50-600 mcg) have been generally well tolerated in the FTIH study, with no emerging safety signals, in healthy, non-pregnant, premenopausal female subjects (Study 201558) [GlaxoSmithKline Document Number 2016N277949_00; see also Section 2.2.1]. Following inhaled administration oxytocin was rapidly absorbed into the systemic circulation (t_{max} ranging from 0.05 to 0.50 h) with systemic exposure (C_{max} and AUC) increasing with inhaled dose in an

[figure not shown]
approximately proportional manner between 200 and 600 mcg. In general, the shape of the observed oxytocin concentration-time profile following inhaled administration was consistent with that following IM administration.

Based on the data from the FTIH study, and assuming that the PK characteristics of IH and IM oxytocin are similar in TSL compared with non-pregnant women, the 400 mcg inhaled dose is predicted to be an effective dose in women in TSL by ensuring that the systemic exposure (Cp10, Cp30 and AUC(0-3 h)) following IH dosing is at least that following IM administration at the approved dose of 10 I.U. This would be based on the adjusted geometric mean ratio (90% Confidence Interval [CI]) treatment comparisons for Cp10, Cp30 and AUC (0-3 h) following 400 mcg IH compared with 10 I.U. IM, namely 1.10 (0.85, 1.43), 1.65 (1.30, 2.09) and 1.27 (1.07, 1.50) respectively in study 201558. The PK parameters (Cp10, Cp30 and AUC(0-3 h)) have been selected to ensure onset and duration of action of the IH product is at least comparable to IM.

The clinical safety and reported AEs with oxytocin correlates to C_{max}, with the C_{max} of 10 I.U. IV representing the upper bounds of what could be considered safe in current clinical practice (AEs include flushing, which can cause a transient decrease in blood pressure and reflex tachycardia; see the Oxytocin Summary of Product Characteristics for more information). The recommendation in the United Kingdom (UK) in clinical practice has been to reduce the IV dose to 5 I.U. IV or administer by a controlled IV infusion [Bolton, 2003].

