7. STUDY ASSESSMENTS AND PROCEDURES

Protocol waivers or exemptions are not allowed with the exception of immediate safety concerns. Therefore, adherence to the study design requirements, including those specified in the Time and Events Table, are essential and required for study conduct.

This section lists the procedures and parameters of each planned study assessment. The exact timing of each assessment is listed in the Time and Events Table in Section 7.1.

The following points must be noted:

- If assessments are scheduled for the same nominal time, THEN the assessments are recommended to occur in the following order:
 1. 12-lead ECG
 2. vital signs
 3. blood draws

Note: The timing of the assessments should allow the blood draw to occur at the exact nominal time.

- The timing and number of planned study assessments, including safety, pharmacokinetic, pharmacodynamic, immunogenic or other assessments may be altered during the course of the study based on newly available data (e.g., to obtain data closer to the time of peak plasma concentrations) to ensure appropriate monitoring.
- The change in timing or addition of time points for any planned study assessments must be documented in a Note to File which is approved by the relevant GSK study team member and then archived in the study sponsor and site study files, but this will not constitute a protocol amendment.
- The Institutional Review Board (IRB)/ Independent Ethics Committee (IEC) will be informed of any safety issues that require alteration of the safety monitoring scheme or amendment of the Informed Consent Form.
- No more than 500 mL of blood will be collected over the duration of the study, including any extra assessments that may be required.

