7.1. Time and Events Table**7.1.1. Time and Events Table – General Overview****Group 1**

Procedure	Study Day			
	Screening ⁴	Main Phase	Follow – Up 1 (approx. 24 hours post dose)	Follow – Up 2 (7-14 days post dose)
Informed Consent and Demography	X			
Brief Physical Examination	X			
Medical history (incl. substance abuse)	X			
Inhaler device training / education session	X			
Laboratory assessments ¹	X			
Vital signs ²	X	X		
Pharmacokinetic blood sample		X		
Oxytocin Administration (IM/IH)		X		
Full blood count		X		
Labour Events Documentation		X		
Device acceptability questionnaire ³		X		
Prior / concomitant medication review	X	X	X	X
AE review		----- continuous review -----		
SAE review		----- continuous review -----		

1. Only required if done as part of routine care. Additional study-specific laboratory assessments not required.
2. Includes blood pressure, heart rate, temperature, respiratory rate
3. Only to be used when randomized to IH oxytocin
4. To be completed after 18th week of pregnancy (based on estimated date of delivery).

Group 2

Procedure	Study Day		
	Screening ⁵	Main Phase	Follow - Up (7-21 days post dose)
Informed Consent and Demography	X		
Brief Physical Examination	X	X	
Medical history	X		
Pregnancy test	X	X	
Alcohol Breath Test, Smokerlyzer, Urine Drug Screen ¹	X	X	
HIV, Hep B and Hep C screen ²	X		
Inhaler device training / education session	X		
Laboratory assessments (including liver chemistries)	X	X	
Immunogenicity sample		X	X
12-lead ECG	X ⁴	X	
Cardiac Telemetry		X	
Vital signs ³	X	X	
Spirometry (FEV-1) ⁴	X	X	
Admission to unit		X	
Pharmacokinetic blood sample	X	X	
Oxytocin Administration (IH or IV)		X	
Prior / concomitant medication review	X	X	X
AE review		----- continuous review -----	
SAE review	----- continuous review -----		
Discharge from unit		X	

1. Smokerlyzer at PI/designee discretion if smoking history in question.
2. If test otherwise performed within 3 months prior to first dose of study treatment, repeat testing at screening is not required.
3. Includes blood pressure, heart rate, temperature, respiratory rate, and SpO2.
4. Performed in triplicate.
5. To be completed within 28 days of randomization.

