7.1.2. Time and Events – Main Phase Procedures**Group 1**

Procedure	Pre-dose	Time post dose										
		3 min	5 min	10 min	15 min	20 min	30 min	1 hr	2 hr	2.5 hr	3 hr	4 hr
Vital signs ¹							X		X			
Pharmacokinetic blood sample	X ²	X	X	X	X	X	X	X	X	X	X	X
Prior medication review	X											
Concomitant medication review		----- continuous review -----										
AE review		----- continuous review -----										
SAE Review		----- continuous review -----										
Device Acceptability Questionnaire ³												X
Full Blood Count	X											X

1. Includes blood pressure, heart rate, temperature, respiratory rate
2. Predose PK sample to be taken immediately prior to administration of study treatment
3. Only to be administered when randomized to IH oxytocin

Group 2 – Sessions 1 and 2

Procedure	Pre-dose	Time Post Dose														
		2 min	3 min	5 min	8 min	10 min	15 min	20 min	30 min	45 min	1 hr	1.5 hr	2 hr	2.5 hr	3 hr	4 hr
Brief Physical Exam	X															
Pregnancy Test	X															
Alcohol Breath Test, Smokerlyzer, Urine Drug Screen ¹	X															
Vital signs ²	X			X			X		X		X					X
12-lead ECG	X	X					X		X	X		X				X
Cardiac Telemetry		-----Continuous-----														
Spirometry ³	X											X				
Pharmacokinetic blood sample	X ⁵	X	X	X	X	X	X	X	X	X	X	X	X	X	X	X
Immunogenicity Sample	X															
Laboratory assessments (including liver chemistries)	X															X
Prior medication review	X															
Concomitant medication review		-----continuous review-----														
AE review		-----continuous review-----														
SAE Review		-----continuous review-----														
Discharge from unit ⁴																X

1. Smokerlyzer at Principal Investigator (PI)/designee discretion if smoking history in question.
2. Includes blood pressure, heart rate, temperature, respiratory rate, and SpO₂
3. FEV 1.0 will be performed in triplicate at each time point. Record all three values on source document, and record best effort in eCRF.
4. Discharge at PI discretion, no sooner than 4-hours post-dose.
5. 3 pre-dose samples: approximately 1 hr pre-dose, 30 minutes pre-dose, and 15 minutes pre-dose

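### Group 1 vital signs are scheduled only at 30 minutes and 2 hours after dosing, so acute change from dosing and any early transient response are not quantified in women in the third stage of labour

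*Protocol*

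**What the plan says.** Protocol 3.1 lists, as a secondary endpoint for Group 1, adverse events together with "absolute values and changes over time of vital signs (blood pressure, heart rate, respiratory rate, temperature"). It does not name the reference value for change. Section 3.2 does so for Group 2, where change is taken from pre-dose.

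Section 7 makes the schedule binding: "The exact timing of each assessment is listed in the Time and Events Table in Section 7.1". In the Group 1 table of 7.1.2 the vital-signs row, footnoted "Includes blood pressure, heart rate, temperature, respiratory rate", is marked at 30 min and at 2 h and nowhere else. The table has a pre-dose column and other procedures use it. The PK row, for instance, carries the footnote "Predose PK sample to be taken immediately prior to administration of study treatment".

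The overview table in 7.1.1 adds one vital-signs reading at screening, footnoted "To be completed after 18th week of pregnancy (based on estimated date of delivery"). Section 4.2 gives the outer limit: "Screening after 18th week of pregnancy (i.e. within 168 days of 1 dosing session").

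Section 4.5 reports inhaled tmax "ranging from 0.05 to 0.50 h" from the first-in-human study and states: "The clinical safety and reported AEs with oxytocin correlates to" Cmax. It names a transient fall in blood pressure and reflex tachycardia among the effects. Section 4.6.1 lists hypotension and tachycardia as risks of the inhaled product.

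**The concern.** The endpoint asks how vital signs change, and the risk that the protocol itself names is short-lived and tied to peak concentration. Measuring such an effect calls for a reading shortly before dosing and at least one while concentrations are near their peak. Group 1 has neither. A value from an antenatal visit, not in labour and possibly months old, is not a usable baseline for an acute drug effect.

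Group 1 is the population for which the product is intended. Section 4.5 accepts that exposure may differ in pregnancy, and the possible increase of the inhaled dose in 6.4.1 applies only to these women. ECG and telemetry are confined to Group 2 (7.3.8 and 7.3.9), so in Group 1 vital signs are the only scheduled cardiovascular measurement.

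**Working it through.** The check sets the schedule against the endpoint. The plan states no figure on this point to reproduce.

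**1. Scheduled times (7.1.2).** The Group 1 vital-signs row has 12 cells: pre-dose plus 11 post-dose times.

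| | Vital signs | PK draws up to 30 min |
|---|---|---|
| Group 1 | 30 min, 2 h | pre-dose, 3, 5, 10, 15, 20, 30 min |
| Group 2 | pre-dose, 5, 15, 30 min, 1 h, 4 h | pre-dose, 2, 3, 5, 8, 10, 15, 20, 30 min |

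The Group 1 marks are in cells 7 and 9. A slip in reading the table is unlikely: the PK row fills all 12 cells, the full-blood-count row is marked at pre-dose and 4 h, and all four protocol versions in the file carry the same vital-signs row. So 0 of the 2 main-phase readings precede dosing and 0 fall before 30 min.

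**2. Age of the only earlier reading.** Inclusion criterion 6 allows 24 weeks from screening to the estimated delivery date: 24 × 7 = 168 days, which agrees with 4.2. For a woman screened at week 18 who labours at 37 to 42 weeks, the gap is (37 − 18) × 7 = 133 days to (42 − 18) × 7 = 168 days. Later screening shortens it, but the reading would still be an antenatal one.

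**3. Position of the first reading relative to the peak.** Inhaled tmax is 0.05 × 60 = 3 min to 0.50 × 60 = 30 min. The 30 min reading sits at the upper end of that range.

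**4. Illustration of what the two readings see.** Assume first-order decay from the peak with the half-life of about 30 min given in 4.6.1. The fraction of peak remaining at time t is 0.5^((t − tmax)/30).

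- At 30 min: tmax 3 min gives 0.5^(27/30) = 0.54; tmax 30 min gives 1.00.
- At 2 h: tmax 3 min gives 0.5^(117/30) = 0.07; tmax 30 min gives 0.5^(90/30) = 0.125.

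The 30 min reading is therefore taken at roughly 54% to 100% of peak concentration, and the 2 h reading at 7% to 13%. The first is not blind to exposure. However, an early peak would already have passed, and there is no near-dose value to compare either reading with.

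**The case against.** The strongest reply is that endpoint and schedule do not formally conflict. Unlike 3.2, section 3.1 does not define change from pre-dose, so the 30 min to 2 h change satisfies the words, and the randomised comparison of absolute values between inhaled and IM needs no baseline. This stands, and it limits the point. A reader might infer that haemodynamic change cannot be measured at all in Group 1; the documents do not support that.

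A reader might also infer that a fall in pressure would simply be missed. That goes too far. Adverse events are reviewed continuously after dosing, 12.3.1 counts clinically significant vital-sign changes as adverse events, and 4.6.1 describes close observation of these women. What is lost is the measured size of a transient that nobody judges clinically significant.

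The timing argument belongs to the inhaled arm. The tmax range comes from inhaled dosing in non-pregnant women. Section 4.5 calls the inhaled and IM profile shapes consistent but gives no IM tmax, so extending the window to the IM arm is inference.

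One can also argue that early haemodynamics were assigned to Group 2, where safety is a primary objective and the same inhaled dose is given with pre-dose, 5 and 15 min readings, ECG and telemetry. That is a reasonable division of effort, but it yields no early data in labouring women.

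Finally, a pre-dose reading is awkward. Section 7.3.6 requires a semi-supine position after 5 minutes of rest, and dosing coincides with or closely follows birth, so within-arm change mixes drug with delivery. This is correct, and the remedy has to allow for it. Sections 7 and 7.3 permit extra time points, but nothing requires them, so they make the remedy easier without supplying it.

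**Conclusion.** The point holds in a limited form. Following the schedule exactly, Group 1 yields two post-dose readings, none before 30 min, and a screening value up to 168 days old. Acute change from dosing, and any blood pressure or heart rate response within the 3 to 30 min inhaled tmax window, is not quantified in women in the third stage of labour.

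The schedule facts need no assumption. The clinical relevance of the window rests on the protocol's own link between adverse effects and Cmax, and on the non-pregnant inhaled tmax carrying over to labour. The decay figures are illustrative only.

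The primary objective is pharmacokinetic and is unaffected. Vital signs share the secondary safety endpoint with adverse events, which can still be counted by arm. This is a gap in one secondary endpoint in the target population, worth closing because doing so is cheap.

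**What to change.** Reconcile 3.1 with the Group 1 table in 7.1.2:

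- Add a pre-dose vital-signs entry, defined as the last observation in labour with its time recorded, and exempt it from the posture and rest condition in 7.3.6. State in 3.1 that this is the reference for change.
- Add one reading within the first 15 min, alongside an existing PK draw (5, 10 or 15 min). Section 7 already sets the order at a shared time point: vital signs before blood, with blood at the exact nominal time.
- State that, because delivery itself alters vital signs, change will be interpreted mainly through the randomised inhaled versus IM comparison and not as a drug effect within an arm.

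Section 7 allows added time points to be documented by Note to File without a protocol amendment, and 7.3 specifically foresees extra vital-sign times. Staff are already drawing blood before dosing and at 3, 5, 10, 15 and 20 min. The cost is one transcribed entry and one extra cuff reading per woman, plus the matching case report form fields. The main drawback is a baseline of non-standard posture and variable timing. Recording its time makes the variable timing visible. With about 10 women per arm, the result will remain descriptive.
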